1.0 Background

It is well established that exercise tolerance is strongly dependent on and limited by the ability to deliver oxygen to skeletal muscle. Thus, it is often inferred that the reduced exercise tolerance commonly seen in extreme environments, including altitude, is a result of a frank limitation in skeletal muscle oxygen delivery. At altitude, the mechanism behind reduced oxygen delivery to exercising muscle is traditionally believed to be a reduced blood content of oxygen (Chapman and Levine, 1999). The primary barrier to adequately oxygenating the arterial blood is the alveolar – capillary interface in the lung, where oxygen must diffuse across the alveolar wall, through the interstitial space, across the pulmonary capillary wall, and ultimately bind with hemoglobin (Dempsey and Wagner, 1999). Any thickening of these tissues or fluid spaces will slow oxygen diffusion and ultimately impair blood oxygenation.

During heavy exercise in many trained individuals, a rise in histamine release from mast cells in the airways is commonly seen, due to the natural irritation of the airways from high levels of ventilation (Youness and Kivinen, 1984) (Figure 1). This causes an inflammatory response in the alveolar wall, increasing the diffusion distance oxygen must travel from the alveoli to arterial blood (Anselme et al., 1994). While during exercise at sea level, a reduced rate of pulmonary oxygen diffusion may not be a limiting factor, at altitude, diffusion of oxygen is already slowed substantially (West, 2012). Therefore, any intervention which could minimize a histamine-mediated inflammatory response could help to maximize arterial blood oxygenation at altitude and defend exercise performance. Cetirizine (Zyrtec®) is a selective H1 receptor antagonist, which blocks histamine binding, thereby minimizing any inflammatory response in the airways (Togias, 2003). Unlike other selective H1 receptor antagonists, like Diphenhydramine (Benadryl®), Cetirizine does not cross the blood-brain barrier as readily, and therefore has minimal side effects (e.g. drowsiness) which could negatively affect exercise performance.

Whether a simple, single intervention of Cetirizine / Zyrtec® use can improve exercise performance of active individuals when acutely exposed to altitude is completely unknown.

2.0 Rationale and Specific Aims

Specific Aim #1 – Determine the effect of Cetirizine (Zyrtec®) on exercise performance and arterial oxygenation with acute exposure to a simulated altitude

For this project, healthy subjects will perform steady state and progressive work rate exercise, endurance performance time trials, and repeated sprint performance time trials in the laboratory at a simulated altitude of 3000m (9900ft) after dosing with 10 mg of Cetirizine or a placebo in a repeated measures design. Non-invasive techniques (pulse oximetry, near-infrared spectroscopy [NIRS]) will be utilized to measure changes in arterial oxyhemoglobin saturation and skeletal muscle oxygenation at the level of the microvasculature during exercise.

It is expected that after Cetirizine, blood and muscle microvascular oxygenation during heavy exercise will improve compared to placebo, ultimately improving exercise performance at altitude.

3.0 Inclusion/Exclusion Criteria

Inclusion criteria:

- Physically active a minimum of 120 minutes a week, as determined by questionnaire
- 18-35 years of age
- Classified as low risk, based on the modified PAR-Q questionnaire, BMI, and non-smoking status
- No history of pulmonary disease and pulmonary function classified as normal, as defined by the following measurements being 80% of predicted values: forced vital capacity (FVC), forced expired volume in one second (FEV1) and FEV1/FVC, according to the American Thoracic Society standards.

Exclusion criteria:

- Current smoker
- Women who are pregnant or could possibly be pregnant
- BMI > 25 kg/m²
- A 'yes' answer to any of the 14 questions on the PAR-Q pre-participation questionnaire
- History of pulmonary disease or <80% of predicted FCV, FEV1 and/or FEV1/FVC.
- A history of renal or liver disease, due to possible interaction effect with Cetirizine
- Currently taking any prescription or over the counter medications for the treatment of allergies, or taking any of the below listed drugs known to have a moderate or higher interaction effect with Cetirizine:

isocarboxazid
tranylcypromine
bosutinib
clobazam
crizotinib
daclatasvir
eliglustat
hyaluronidase
lomitapide
lurasidone
ombitasvir/paritaprevir/ritonavir
phenelzine
ponatinib
ritonavir
vemurafenib

4.0 Enrollment/Randomization

Subjects will be recruited by flyers posted in the School of Public Health building and local cycle shops. Subjects will also be recruited by direct email to known cyclists and endurance athletes who are either a) contacts of the PI and co-I, or b) members of club or fraternity cycling teams.

5.0 Study Procedures

[figure not shown]
Study design: Subjects will be asked to report to the laboratory on a three occasions, separated by a minimum of 48 hours and a maximum of 14 days. For each subject, all testing sessions will be performed at the same time of day. Prior to each testing session, subjects will be asked to abstain from caffeine consumption for 12 hours. Subjects will also be asked to avoid alcohol consumption for 24 hours before testing, be at least 3-hour post prandial and avoid high-intensity exercise during the 24 hours leading to the exercise testing. Finally, subjects will be asked to consume a similar diet the night before, and the morning of, Sessions 2 and 3.

The first session of testing includes: informed consent completion, completion of a general questionnaire, completion of a standard medical questionnaire, measures of height and weight, measures of body composition, resting pulmonary function testing, completion of a maximal oxygen uptake test on a cycle ergometer (in normoxia) with measures of respiratory flow-volume characteristics, and familiarization with the 5km cycle ergometry time trial (TT) in hypoxia (14.3% O₂, simulating 3000m). This session is expected to take approximately 60-90 minutes.

The 2nd and 3rd sessions will include Cetirizine (10 mg) or placebo ingestion, 60 minutes of rest (time required to reach peak Cetirizine plasma levels), a blood draw to measure plasma histamine levels, a brief warm-up, two 5-minute constant-load cycle ergometry exercise bouts at moderate intensity in hypoxia with 5-minute of passive recovery following each exercise bout, a 5km cycle ergometry TT in hypoxia, and a post-exercise blood draw to measure plasma histamine levels. These sessions are expected to take approximately 120 minutes each.

During the hour between Cetirizine / placebo ingestion and the beginning of the testing trial, subjects will be allowed to rest comfortably in the lab. Sessions 2 and 3 will be randomized and counterbalanced.

A graphical timeline is below:

Study procedures: (Session 1) after completion of informed consent documents and questionnaires, height and weight will be measured. Body composition will be measured by bioelectrical impedance. Resting pulmonary function will then be performed as described by the American Thoracic Society (specific procedures and measurements are detailed under *“Resting Pulmonary Function Testing”* below). Following these measurements, subjects will be allowed to warm up on the cycle ergometer at a self-selected speed for 10 minutes. Subjects will then be fitted with a chest strap heart rate monitor and an oro-nasal face mask. A pulse oximeter sensor will also be placed on the subject's forehead to non-invasively measure arterial oxyhemoglobin saturation. Optodes from a near-infrared spectroscopy device will be placed on the subject's thigh and secured with a Velcro strap, in order to non-invasively measure oxygenated and deoxygenated heme-O₂ carriers in the skeletal muscle.

The maximal oxygen uptake test will begin with subjects pedaling at 50W, with subjects instructed to keep RPMs between 80 and 110. The workload will increase by 25W each minute until volitional exhaustion or until RPMs fall below 70 for more than five seconds. After completion of the maximal oxygen uptake test and following a 15-minute rest period, subjects will be asked to complete a familiarization 5km time trial on the cycle ergometer breathing a hypoxic inspirate (14.3% O₂, simulating 3000m) in as short of a time as possible (most subjects require between 8 and 12 minutes). Subjects will be able to self-select cadence and resistance on the ergometer.

(Session 2 and 3) Upon arrival at the lab, subject will be given either 10 mg of Cetirizine in pill form or a placebo (10 mg of gelatin in capsule form). Subjects will be allowed to sit comfortably or lie down for 60 minutes. Following this rest period, approximately 5 ml of blood will be drawn from an antecubital vein. Subjects will then be allowed to warm up

on the cycle ergometer at a self-selected speed for 10 minutes. Following the warm-up, subjects will be fitted with a chest strap heart rate monitor, an oro-nasal face mask, a pulse oximeter sensor, and near-infrared spectroscopy optodes. Subjects will then be asked to complete two 5-minute cycling bouts at a constant, moderate intensity (as will be determined individually according to each subject's maximal oxygen uptake test performed on Session 1, details below). Subjects will be allowed 5 minutes of passive recovery after each of the 5-minute cycling bouts. Following the second recovery period, subjects will be asked to ride 5km, completing the distance in as short of a time as possible. Subjects will be allowed to shift gears on the bike at will and pedal at any RPM desired. Feedback on distance completed will be shown on a video monitor and verbally announced every 1km. During the TT, respiratory flow-volume measures will be completed by having the subjects complete two inspiratory capacity (IC) maneuvers near the end of each kilometer of the TT. Immediately following the TT, approximately 5 ml of blood will be drawn from an antecubital vein.

Demographic and screening variables: Age, height, weight, sex, body mass index, body composition (estimated percent lean body mass and fat mass), pulmonary function measures (total lung capacity, vital capacity, forced expiratory volume in one second, lung diffusing capacity, and maximal voluntary ventilation).

Dependent variables: exercise metabolic measures (VO₂, VCO₂, ventilation, heart rate), dyspnea and rating of perceived exertion during the 5km TT, time to completion of the 5km TT, power output during the 5km TT, muscle oxygenation, plasma histamine levels.

Specific Measures:

Height and weight: Height will be measured using a standard wall mounted, sliding height measuring board (stadiometer). Weight will be measured by an electronic scale.

Body composition: Subject stands in bare feet on an electrode imbedded scale (Tanita) and holds on to electrode imbedded handles. An unnoticeable electrical current is passed through the subject for 2 seconds, from which resistance to electrical flow is measured and body composition is estimated.

Resting Pulmonary Function Testing: Subjects will be asked to sit in a comfortable chair for approximately 10 minutes of rest. Tests of breathing function are performed as described by the American Thoracic Society. These tests include the measurement of total lung capacity (the volume of air the lungs can hold), vital capacity (the volume of air that can pushed out with one maximal breath), FEV1 (the volume of air that can be forcefully breathed out in one second), maximal inspiratory and expiratory flow rates (used to generate maximal flow-volume loops), lung diffusing capacity and maximal voluntary ventilation (MVV; the maximal volume of air that can breathed in 12 seconds). For all of these procedures, the subject will then be fitted with a rubber mouthpiece and noseclip.

Respiratory flow-volume measures: At a number of time points during the exercise trials subjects will be asked to complete two inspiratory capacity (IC) maneuvers by inspiring maximally once and then continuing to breathe normally. For the maximal oxygen uptake test the IC maneuver will be performed near the end of each minute of exercise, and for the TT near the end of every 1km.

Near-infrared spectroscopy (NIRS) measures: Near-infrared Spectroscopy (NIRS): Frequency domain NIRS will be used in vivo to non-invasively determine the volume of heme-O₂ carriers in the exercising muscle microcirculation. During the constant-load and 5km TT, the device probe will be placed on the surface of the right vastus lateralis. The device probe will be secured with a Velcro strap and wrapped with a cloth bandage to prevent movement and light leakage. Position of the device probe will be marked with indelible marker and photographed to match placement between trials.

Rating of perceived effort: At the completion of each km during the 5km TT subject will be shown a chart and asked to point to a rating of perceived breathlessness (dyspnea) on a scale of 0-10 (modified Borg scale). Subjects will be familiarized with this scale prior to the TT and will be told that 0 implies no “noticeable breathing effort above what occurs at rest” and 10 indicates “maximal ventilatory effort”. Additionally, at the end of each km, subjects will be asked to point to a chart to indicate their overall rating of perceived exertion (RPE; 0-10 modified Borg scale where 0 in implies “no effort” and 10 indicates “maximal effort”).

Cetirizine and placebo.

Upon arrival at the laboratory for Sessions 2 and 3, subjects will be asked to ingest a pill containing 10mg of Cetirizine or a gelatin placebo. Black colored (e.g. non-opaque) size 1 gelatin capsules will be purchased commercially. For placebo, the capsules will be filled with 10 mg of sugar-free gelatin, purchased from a local grocery store. Cetirizine will be purchased over-the-counter, and the 10mg pill will be encapsulated within the same black colored size 1 gelatin capsule as the placebo. The treatment will be double-blinded and the order will be randomized and counter-balanced. Pharmacokinetics of Cetirizine indicate peak plasma levels are achieved within 60 min, and as subjects will be at least 3 hours post-prandial, will not be delayed by recent diet.

Maximal oxygen uptake: The subject will be asked to warm up on the cycle ergometer for 10 minutes at a comfortable, self-selected pace. Subjects will be fitted with a) an oronasal face mask which covers the nose and mouth, b) a chest strap heart rate monitor, and c) a pulse oximeter sensor will also be placed on the subject's forehead to non-invasively measure arterial oxygen content. The subject will then be asked to pedal at a cadence between 80 and 110 rpm at a workload of 50W. The workload will be increased by 25W every minute until volitional exhaustion or until RPMs fall below 70 for 3 seconds. Expired air from the face mask is collected in a tube for the determination of oxygen content, CO₂ content, and expired ventilatory volumes.

Constant-load cycling: In sessions #2 and #3, subjects will be asked to complete five minutes of cycling at submaximal workloads equal to 60% and 75% of VO₂max, as determined in session #1. Subjects will have five minutes of passive rest after each 5-minute exercise bout.

5km cycle performance trial: Subject will be asked to complete 5km on the cycle ergometer in as short a time as possible (fit individuals typically take between 8 and 12 minutes). Subjects will be free to shift gears on the cycle and pedal at any cadence desired. Subjects will be given visual feedback on distance travelled and verbal feedback every 1km.

Hypoxic inspirate: Altitude will be simulated by breathing a hypoxic inspirate. A commercially available, portable nitrogen generator (Colorado Altitude Training Systems) will be used to generate nitrogen rich air, in order to decrease the O₂ content to the specified level. The nitrogen generator will be set to produce an outflow of 14.3% O₂, equivalent to an altitude of 3000m / 9900 ft. Note that the mechanical design limits of the nitrogen generator only allows for a minimal O₂ level of 14.3%. Additionally, our laboratory O₂ analyzer will constantly monitor and record inspired oxygen levels. Hypoxic gas from the generator will be collected in two large meteorological balloons, to serve as the inspired air reservoir.

Blood sampling: In each of Sessions 2 and 3, subjects will be asked to give two blood samples of ~ 2-5 ml each: one prior to beginning cycle exercise, and one after completing the 5km time trial. Blood will be taken via routine venipuncture procedure from an antecubital vein using a 22g or smaller needle and a sodium EDTA treated (lavender top) vacutainer. Standard precautions will be used, and an experienced investigator will perform the venipuncture. Subjects will be free to choose the arm used for each venipuncture.

6.0 Reporting of Adverse Events or Unanticipated Problems involving Risk to Participants or Others

The primary investigator will report the frequency of monitoring and dates, summary of adverse events, assessment of external factors that impact safety of subjects, summary of subject privacy and research data confidentiality, and changes to the risk-benefit ratio. Adverse events include death, an injury requiring hospitalization, loss of information containing identifiable records, an unanticipated experience associated with intensive exercise, and other related events. Our intention is that the data from this study may be used in characterizing the athletic population, and may be used in longitudinal comparisons.

In the event of an adverse event, the PI will report immediately to and cooperate with the IRB in any necessary investigation. After two adverse events, the protocol will be evaluated for possible modification.

The primary investigator is responsible for the data and safety monitoring. In addition, [name], a faculty member within the Department of Kinesiology, will serve as an independent data safety monitor for the study. Data will be analyzed by subject number. Thus, analysis of data will be done without any identifying features to individuals. Statistical software will be used to analyze data for significance. Results will be reported through traditional scientific outlets such as journals and presentations. Communication with the IRB regarding safety will be reported directly by the primary investigator.

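### The placebo fill is set at 10 mg, which equals the pill's drug content and not the mass of the whole pill, so the capsules as written differ in weight unless the pill has no excipient

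*Combined protocol and SAP*

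**What the plan says.** The preparation rule is in section 5.0 of the combined protocol and SAP, in the paragraph on cetirizine and placebo.

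- **Shells.** "Black colored (e.g. non-opaque) size 1 gelatin capsules will be purchased commercially". Both products go into them.
- **Active capsule.** "Cetirizine will be purchased over-the-counter", and "the 10mg pill will be encapsulated within the same black colored size 1 gelatin capsule as the placebo". The same paragraph says that "subjects will be asked to ingest a pill containing 10mg of Cetirizine or a gelatin placebo", so 10 mg is the amount of drug in the pill.
- **Placebo capsule.** "For placebo, the capsules will be filled with 10 mg of sugar-free gelatin". No other content is named.
- **Blinding.** "The treatment will be double-blinded", with randomized and counterbalanced order.

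The earlier description of Sessions 2 and 3, also in section 5.0, repeats the 10 mg placebo figure: "subject will be given either 10 mg of Cetirizine in pill form or a placebo (10 mg of gelatin in capsule form".

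The documents do not give the total mass or dimensions of the pill or the physical form of the gelatin. They mention no filler around the pill, no target capsule weight and no check that the capsules are alike in the hand. They also do not say who prepares the capsules or hands them over.

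**The concern.** Apart from randomized order, the identical shell is the only blinding measure described, and it deals with appearance alone. If the written rule is followed, one capsule holds a solid pill and the other a small amount of gelatin, and they have the same weight only in a special case.

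The blind matters here for three reasons. Each subject takes both products. Section 2.0 states in advance that cetirizine is expected to improve oxygenation and performance. And several dependent variables are self-paced or self-reported: "dyspnea and rating of perceived exertion during the 5km TT, time to completion of the 5km TT, power output during the 5km TT". A belief about which capsule was taken could affect how hard a subject rides or how a subject rates effort and breathlessness. The same applies to staff who are in contact with the subject during the time trial, if they have handled several capsules and sensed a difference.

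**Working it through.** The plan gives no capsule weight, so there is no figure of its own to reproduce. The check compares the contents by mass.

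**Inputs**

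- Shell mass *s*: not given, but the same for both products (section 5.0).
- Placebo fill: 10 mg (section 5.0, in two places).
- Drug in the active pill: 10 mg (section 5.0).
- Whole-pill mass *t*: not given, so assumed over a range.

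**Formula**

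Active capsule = *s* + *t*. Placebo capsule = *s* + 10.

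Gap = (*s* + *t*) − (*s* + 10) = *t* − 10 mg.

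The shell cancels, so no assumption about it is needed. Since 10 mg of the pill is drug, *t* − 10 is also the mass of the inactive ingredients.

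**Results**

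| Assumed pill mass *t* | Gap = *t* − 10 | Pill mass relative to the placebo fill = *t* / 10 |
|---|---|---|
| 10 mg (no excipient) | 0 mg | 1 |
| 50 mg | 40 mg | 5 |
| 100 mg | 90 mg | 10 |
| 200 mg | 190 mg | 20 |

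The stated fill gives equal weights in the first row only. For any heavier pill, following the protocol exactly produces unequal capsules.

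**Form.** The active capsule contains a single solid pill and the placebo a small gelatin fill. The two could therefore differ in feel or sound as well as weight. The documents do not describe the gelatin well enough to say how much.

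**The case against.** The strongest reply is that no consequence has been shown. The tablet mass is assumed, no detection threshold is available, and even a 190 mg gap is not known to be noticeable. Sessions are 48 hours to 14 days apart, and nothing in the plan has a subject holding both capsules at once. At Session 2 there is no earlier study capsule to compare with; at Session 3 the comparison is from memory. Noticing a difference would not by itself reveal which capsule is active. Color and size are already matched and the order is counterbalanced.

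All of this stands, and it limits the point to a risk. It does not remove the point. The plan does more than omit a preparation detail: it states a fill that fails to match unless the pill is pure drug. The interval between sessions also does not prevent a comparison by someone who handles several capsules, although the documents do not say whether anyone does.

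A reader might go further in three ways that the documents do not support:

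- **That oxygen saturation and plasma histamine are compromised too.** This needs a chain from noticing the capsule, to a belief about treatment, to changed pacing, to changed ventilation, to a changed measurement. Section 8.0 says only that saturation is obtained at each kilometer, and section 1.0 links histamine release to high ventilation. Neither supports the earlier links.
- **That the contents can be seen.** The word non-opaque, applied to a black capsule, reads as a slip.
- **That one product is a bare pill and the other a capsule.** The Sessions 2 and 3 text can be read that way, but the cetirizine and placebo paragraph puts both in capsules.

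**Conclusion.** The point holds as a preventable weakness in the blinding procedure and should be addressed. The shells match; the contents, as written, do not. The weight gap is the pill's excipient mass: 40 to 190 mg for an assumed tablet of 50 to 200 mg, and zero only for a pill without excipient. That the real pill weighs more than 10 mg is an inference from its description as a pill containing that amount of drug. The exposed outcomes are chiefly 5 km time, power output, perceived exertion and dyspnea.

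A reader might infer that the trial is in effect unblinded or that its results would favor cetirizine. The documents show neither: detection is not established, and the size and direction of any bias are unknown. Confidence is high on the text and the arithmetic, and medium on practical importance.

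**What to change.** In section 5.0, replace the 10 mg placebo fill with an inert fill that brings the placebo capsule to the weight of the finished active capsule within a stated tolerance. Before use, check that the two cannot be told apart by weight, feel or sound, and record the result.

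Equal weight does not guarantee equal feel or sound. If filling only the placebo fails the check, put the same inert filler in both capsules and confirm that it is compatible with the stated 60-minute interval between ingestion and testing.

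Two clerical edits belong with this: correct non-opaque, and reconcile the pill form and capsule form wording for Sessions 2 and 3 with the paragraph that encapsulates both products.

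The cost is some inert filler, slightly longer capsule preparation for weighing and the handling check, and the wording edits. Filling only the placebo leaves the active capsule unchanged. The compatibility check is an added cost only if filler is needed in both capsules.
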